1.1 Statistical and analytical plans

The planned analysis is described in Section 9 (Data Analysis) of the study protocol which is available in Appendix 16.1.1 of the CSR.

This document covers statistical and analytical plans for the primary endpoint analysis i.e. the resolution of the index flare at the time of randomization and the absence of incident flares over the first 16 weeks after randomization, at Week 16 interim analysis but also covers the analyses for the Week 40 interim analysis and the final analysis after database lock. The data collected in this study up to the time of the Week 16 interim analysis will be part of the marketing authorization submission package of the ACZ885N project. All data collected up to Week 16 will be analyzed in the Week 16 interim analysis.

This study consists of 3 cohorts (one cohort per condition: TNF-receptor Associated Periodic Syndrome (TRAPS), Hyper IgD Syndrome (HIDS) and colchicine resistant Familial Mediterranean Fever (crFMF)), and 4 study epochs.

Each cohort will follow the same study design across the 4 epochs:

- A screening epoch to assess patients' eligibility of up to 12 weeks duration (Epoch 1)
- A randomized treatment epoch (Epoch 2) of 16 weeks which will provide efficacy and safety data in a double-blind placebo-controlled parallel-arm setting. This randomized treatment epoch will include 2 possible escape options: Blinded escape (from Day 8 to Day 28), Open-label treatment (from Day 29 to Day 112)
- A randomized withdrawal epoch (Epoch 3) of 24 weeks where Canakinumab responder patients will be re-randomized to canakinumab 150 mg q8w or Placebo
- An open-label treatment epoch (Epoch 4) of 72 weeks to collect long-term safety data for canakinumab.

In order to provide access to treatment, roll-over TRAPS patients previously participating in clinical study CACZ885D2203 and/or the subsequent Multiple Patient Program (MPP) treatment plan CACZ885D2207M will be allowed to enter the study in randomized withdrawal epoch (Epoch 3) and the Japanese crFMF patients with non-exon 10 mutations or patients >28 days but <2 years old (with bodyweight ≥ 3.75 kg) will enter the study in the open-label arm of randomized treatment epoch (Epoch 2). The non-randomized patient group including Japanese crFMF patients with non-exon 10 mutations and patients >28 days but <2 years old will follow the following study design across the 4 epochs:

- a. A screening epoch to assess patients' eligibility of up to 12 weeks duration (Epoch 1)
- b. An open-label epoch of 16 weeks (Epoch 2)
- c. An open-label epoch of 24 weeks (Epoch 3)

- d. An open-label treatment epoch of 72 weeks to collect long-term safety data for canakinumab (Epoch 4)

All data will be analyzed separately for each independent cohort (TRAPS, HIDS, crFMF).

The purpose of the study is to provide evidence supporting answers to following questions. The data will be analyzed by Epoch:

1. Whether canakinumab at a starting dose of 150mg s.c. (or 2mg/kg for patients ≤ 40 kg) administered every 4 weeks is able to induce and maintain a clinically meaningful reduction of disease activity defined as resolution of the index flare at Day 15 and no new disease flares over 16 weeks of treatment in a greater proportion of patients with TRAPS, HIDS, or crFMF compared to placebo (Data from Epoch 2)
2. Whether, in patients responding to the initial dosing regimen of every 4 weeks, canakinumab will maintain its clinical efficacy if administered at a reduced dosing interval of 150mg s.c. (or 2mg/kg for patients ≤ 40 kg) every 8 weeks. (Data from epoch 3 and 4)

Safety data for the subgroup of patients coming from ACZ885D2203 and/or the subsequent Multiple Patient Program (MPP) treatment plan CACZ885D2207M collected in Epoch 3 and 4 will separately be reported from the other patients who will be screened and randomized in Epoch 2.

Safety data for the subgroup of canakinumab naïve Japanese crFMF patients with non-exon 10 mutations, and patients >28 days but <2 years old, collected in Epoch 2, 3 and 4 will separately be reported from the other patients who will be screened and randomized in Epoch 2.

Summary statistics for continuous variables will include N, mean, standard deviation, minimum, lower quartile, median, upper quartile, maximum, and number of patients with non-missing data (n). Summary statistics for discrete variables will be presented in contingency tables and will include absolute and relative frequencies.

If not otherwise specified, p-values will be presented as two-sided p-values and two-sided confidence intervals will be displayed.

All listings will be presented by cohort and treatment sequence.

1.2 Subjects and treatments

The following analysis sets will be used for the data analysis.

The **Randomized Set** Epoch 2 will consist of all patients who are randomized in the randomized treatment epoch (Epoch 2).

The **Randomized Set** Epoch 3 will consist of all patients who received canakinumab drug in epoch 2 and are responders at week 16 and who are re-randomized in the randomized withdrawal epoch (Epoch 3).

Unless otherwise specified, mis-randomized patients (mis-randomized in IRT) will be excluded from the randomized set. (Mis-randomized patients are defined as cases where IRT contacts were made by the site either prematurely or inappropriately prior to confirmation of the patient's final randomization eligibility and no study medication was administered to the patient).

The **Full Analysis Set (FAS)** Epoch 2 will consist of all randomized patients in the randomized treatment epoch who received at least one dose of study drug in epoch 2. Following the intent-to-treat principle, patients will be analyzed according to the treatment they were assigned to at randomization.

The **Full Analysis Set (FAS)** Epoch 3 will consist of all patients in the randomized withdrawal epoch who received at least one dose of study drug.

The **Safety Set** Epoch 2 will consist of all patients that received study treatment in Epoch 2. Patients will be analyzed according to treatment received. Of note, the statement that a subject had no AEs also constitutes a safety assessment.

The **Safety Set** Epoch 3 will consist of all patients that received study treatment in Epoch 3. Patients will be analyzed according to treatment received. Of note, the statement that a subject had no AEs also constitutes a safety assessment.

The **Safety Set** Epoch 4 will consist of all patients that received study treatment in Epoch 4. Patients will be analyzed according to treatment received. Of note, the statement that a subject had no AEs also constitutes a safety assessment.

The **Per-protocol Set (PPS)** Epoch 2 will consist of all patients in the FAS Epoch 2 who do not fulfill any criteria that could potentially confound the interpretation of analyses conducted on the FAS.

The protocol deviation (PD) population codes leading to exclusion from Per-protocol set are presented in [Table 1-1](#). In addition, subjects receiving a single add-on injection before day 15 despite they don't fulfill criterion for add-on injection from Day 8 to Day 14 were excluded from Per-protocol set.

An analysis based on the per-protocol set will be performed as additional sensitivity analysis. Protocol deviations for exclusion from a per-protocol analysis are defined in [Table 1-1](#).

Table 1-1 Subject classification rules

Analysis set	PD Categories Codes that cause subject to be excluded	Non-PD criteria that cause a subject to be excluded
Randomization set	INC01,INC02,INC20	Mis-randomized subject
FAS Epoch 2(Full Analysis Set)	INC01,INC02,INC20, TRT02	NA
FAS Epoch 3(Full Analysis Set)	INC01,INC02,INC20, TRT02	NA
Safety Epoch 2	INC02, TRT02	NA
Safety Epoch 3	INC02, TRT02	NA
Safety Epoch 4	INC02, TRT02	NA
Per-protocol Epoch 2	See notes*	1) subjects receiving a single add-on injection before day 15 despite they don't fulfill criterion for add-on injection from Day 8 to Day 14 2) subjects taking biologics after taking study medication and don't discontinue study drug

*the following are used to define Per-protocol analysis set:

Exclude the following

INCLXX: TRAPs (INC01,INCL02, INCL06, INCL07, INC20), HIDs(INC01, INCL02, INCL11, INCL12, INC20), crFMF(INC01, INCL02, INCL15, INCL18, INCL19, INC20)

TRTXX: TRT02, TRT07, TRT26

Definition of responders

Definition of responders in epoch 2: canakinumab treated patients in Epoch 2 who maintain a clinically meaningful response (absence of new flares) until week 16 from the time of the resolution of the index flare at day 15. All patients randomized to placebo at baseline and completing the randomized treatment epoch (Epoch 2) without any re-flare will be considered placebo-responders.

Definition of non-responders in epoch 2: In the randomized treatment epoch (Epoch 2), patients needing dose escalation in the canakinumab arms, or escape from Placebo arms to canakinumab, or discontinued from the study due to any reason prior to evaluating the primary endpoint at week 16 will be considered as non-responder in epoch 2.

Definition of responders in epoch 3: Responder in the Randomized withdrawal epoch (epoch 3) is defined as patients having no flare(s) between week 16 and week 40.

Definition of responders in epoch 4: Responders in the epoch 4 are defined as patients having no flare(s) between week 40 and end of the study.

1.3 Treatment group definitions

The following study epoch will be considered for analysis:

- **Epoch 2:** A randomized treatment epoch of 16 weeks. This randomized treatment epoch will include 2 possible escape options: Blinded escape, Open-label treatment
- **Epoch 3:** A randomized withdrawal epoch of 24 weeks

- **Epoch 4:** An open-label treatment epoch of 72 weeks.

Treatment groups for analysis will include:

Randomized treatment epoch (Epoch 2):

Treatment arms for the primary and secondary efficacy analyses will only include canakinumab 150 mg sc q4w and placebo.

Other efficacy and safety data will be displayed in Epoch 2 in the following way:

- Patients being randomized and not having a flare in epoch 2 (and not having received add-on dose or any up-titration)
- Patients being randomized and having at least one flare in epoch 2 and having been up-titrated only once (or received add-on dose) (150mg q4->300mg q4; Placebo->150mg q4)
- Patients being randomized and having at least one flare in epoch 2 and having been up-titrated at least twice (Placebo->300mg q4)

----- No flare ----- ----- >= 1 Flare -----

Randomized	Open –label arm			
150mg q4	Placebo	150mg q4->300mg q4	Pla->150mg q4	Pla->150mg q4->300mg q4

Randomized withdrawal epoch (Epoch 3):

As one of the objectives in epoch 3 is to look at the maintenance of efficacy, patients will be categorized in two groups: those being randomized and keeping their initial treatment arm until the end of epoch 3 (i.e. no having a flare) and the other patients where the cumulative dose (in mg) over the 24 weeks will be analyzed.

Safety and efficacy data will be displayed in Epoch 3 in the following way:

- Re-randomized & no up-titration	----	Cumulative dose in mg over 24 weeks	----	
150mg q8	Placebo	<600mg	600mg - <1200mg	≥1200mg

[figure not shown]
The cut-offs of 600mg, 1200mg were decided based on all options for cumulative dose over 24 weeks depending on the number of flares and initial dose regimen at start of epoch 3.

Example on how the cumulative dose is calculated over the 24 weeks:

Considering a patient taking initially 150 mg q8w at start of epoch 3 and having only one flare in epoch 3 then the patient will up titrate to 150 mg q4w. Here are the different cases. The first line shows the initial schedule with no flare. If no flare, the patient receives 3 injections of 150 mg each so a total of 450 mg over 24 weeks, from Day 113 to Day 281, with no dose at day 281 (belongs to epoch 4).

	Day 113	Day 141	Day 169	Day 197	Day 225	Day 253	Cumulative dose in mg
Dose: 150mg q8 with no flare	X 150mg		X 150mg		X 150mg		450mg
1 flare between D225- D253	X 150mg		X 150mg		X 150mg	X 150mg	600mg
1 flare between D197- D225	X 150mg		X 150mg		X 150mg	X 150mg	600mg
1 flare between D169- D197	X 150mg		X 150mg	X 150mg	X 150mg	X 150mg	750mg
1 flare between D141- D169	X 150mg		X 150mg	X 150mg	X 150mg	X 150mg	750mg
1 flare between D113- D141	X 150mg	X 150mg	X 150mg	X 150mg	X 150mg	X 150mg	900mg

Therefore for a patient taking initially 150mg q8w at the start of epoch 3 and having one flare in epoch 3, the range of cumulative dose over 24 weeks will be [600 mg-900 mg].

Notes: 1. Earlier the flare occurs, higher the cumulative dose is
2. More flares => increase of cumulative dose, but stable after 5 flares

Cumulative dose calculation for epoch 3:

For Patients weighing ≥ 7.5 kg and ≤ 40 kg, the dose is derived in mg/kg ie. Actual total dose (ml) $\times 150$ mg / Weight(kg) at visit.

- If the sum of the dose (mg/kg) in Epoch 3 is ≤ 7 mg/kg then the patient will be assigned to the dose level category <600 mg.
- If the sum of the dose (mg/kg) in Epoch 3 is >7 mg/kg - ≤ 15 mg/kg then the patient will be assigned to the dose level category ≥ 600 mg- <1200 mg.
- If the sum of the dose (mg/kg) in Epoch 3 is >15 mg/kg then the patient will be assigned to the dose level category ≥ 1200 mg.

For Patients weighing <7.5 kg, the dose is derived in mg/kg ie. Actual total dose (ml) $\times 75$ mg / Weight(kg) at visit.

[figure not shown]
- If the sum of the dose (mg/kg) in Epoch 3 is ≤ 7 mg/kg then the patient will be assigned to the dose level category <600 mg.
- If the sum of the dose (mg/kg) in Epoch 3 is >7 mg/kg - ≤ 15 mg/kg then the patient will be assigned to the dose level category ≥ 600 mg- <1200 mg.
- If the sum of the dose (mg/kg) in Epoch 3 is >15 mg/kg then the patient will be assigned to the dose level category ≥ 1200 mg.

Open-label treatment epoch (Epoch 4):

As few patients are expected having no flare in epoch 4 for 72 weeks, then safety and efficacy data will be displayed using the cumulative dose over the 72 weeks in Epoch 4 in the following way:

----- Cumulative dose in mg over 72 weeks -----
<2700mg $\geq 2700\text{mg} - < 5400\text{mg}$ $\geq 5400\text{ mg}$

The cut-offs of 2700mg, and 5400mg were decided based on all options for cumulative dose over 72 weeks depending on the number of flares and initial dose regimen at start of epoch 4. The first group could be considered as patients taking initially 150mg q8w at start of epoch 4 with or without flare over 72 weeks, the second one grouping patients taking initially 150mg q4w or 300mg q8w at start of epoch 4 with or without flare over 72 weeks and the last one patients taking initially 300mg q4 with or without flare over 72 weeks.

Roll-over patients from ACZ885D2203/ CACZ885D2207M and naïve Japanese crFMF patients with non-exon 10 mutations and patients >28 days but <2 years old

Data for the subgroup of patients coming from ACZ885D2203 and/or the subsequent Multiple Patient Program (MPP) treatment plan CACZ885D2207M collected in Epoch 3 as well as canakinumab naïve Japanese crFMF patients with non-exon 10 mutations and patients >28 days but <2 years old collected in Epoch 2 and Epoch 3, will separately be reported from the other patients who will be screened and randomized in Epoch 2. For subgroup 1: Roll-over patients from ACZ885D2203/ CACZ885D2207M:

In epoch 3, for this subgroup of patients safety and efficacy data will be tabulated as follows:

----- Cumulative dose in mg over 24 weeks -----
<600mg 600mg - <1200mg $\geq 1200\text{mg}$

In epoch 4, this subgroup of patients will be reported together with the other patients as follows:

----- Cumulative dose in mg over 72 weeks -----

<2700mg \geq 2700mg- <5400mg \geq 5400 mg

For subgroup 2: Naïve Japanese crFMF patients with non-exon 10 mutations and patients >28 days but <2 years old:

Patient Demographics & other baseline characteristics and Adverse events data for this subgroup will be tabulated under one treatment group ACZ885. All other safety and efficacy data will be listed under one treatment group ACZ885 in epoch 2 and epoch 3. This subgroup of patients will also be reported together with the other patients in epoch 4 using same cumulative dose categories.

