1.4 Summary of the analyses

Table 1-2 Analysis by Epoch

Endpoint/analysis	Epoch			
	Epoch 2 (restricted to initial randomized treatment arms)	Epoch 2	Epoch 3	Epoch 4
Patient disposition	X	X	X	X
Demography & baseline characteristics	X	X	X	X
Medical history	X			
Previous & concomitant medication	X	X	X	X
Surgeries and medical procedures		X	X	X
Rescue medications	X	X	X	X
Study medication: duration of exposure	X	X	X	X
Proportion of responders at week 16	X			
Supportive analysis using SAA	X			
patients who achieve a PGA < 2 at Week 16	X			
Serologic remission at week 16	X			
Normalized SAA	X			
Responder in epoch 3 (only for canakinumab responder in epoch 2)			X	
CRP		X	X	X
PGA		X	X	X
PPGA		X	X	X
Physician's severity assessment of disease signs and symptoms over time		X	X	X
Fever		X	X	X
Blinded escape	X			
Time to new flare			X	
AIDAI	X	X	X	
SF-12	X	X	X	
CHQ-PF50	X	X	X	
SDS v3	X	X	X	
Total IL-1 β		X	X	X
Adverse events		X	X	X
Laboratory data		X	X	X
Vital signs		X	X	X
ECG		X	X	X

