1.13.1 Adverse events

Adverse events will be coded using the MedDRA dictionary that provides the primary system organ class and preferred term information.

Adverse events will be summarized by presenting, for each cohort, epoch, initial randomized treatment and treatment sequence (as defined in [section 1.3](#)), the number and percentage of patients having any adverse event, having any adverse event in each primary system organ class and having each individual adverse event based on the preferred term. All other information collected (e.g. severity, relationship to study treatment) will be tabulated and listed as appropriate.

Adverse events will also be summarized by standardized MedDRA query (SMQ).

Exposure adjusted incidence rate of adverse events by primary system organ class and preferred term will be presented by epoch and according to the actual dose the patient receives.

Deaths, serious adverse events, and adverse events leading to discontinuation of study treatment will be summarized by primary system organ class and preferred term and listings will be provided.

Adverse events of special interest including identified and potential risks and adjudicated malignancy and infection events will be listed and summarized for each cohort, epoch and treatment group (as defined in [section 1.3](#)).

In addition, summary of adverse events and serious adverse events will be presented in combining the three cohorts. Adverse events occurring in follow-up period after discontinuation of study will be listed but not summarized in tables.

For the final analysis, AE/SAE will be reported using data after patients taking ACZ885 starting from epoch 2 to end of epoch 4.

For the legal requirements of ClinicalTrials.gov and EudraCT, two required tables on any ACZ group adverse events which are not serious adverse events with an incidence greater than 5% and on any ACZ group serious adverse events and SAE suspected to be related to study treatment will be provided by system organ class and preferred term on the safety set population.

If for a same patient, several consecutive AEs (irrespective of study treatment causality, seriousness and severity) occurred with the same SOC and PT:

- a single occurrence will be counted if there is ≤ 1 day gap between the end date of the preceding AE and the start date of the consecutive AE

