1.13.3 Laboratory data

Laboratory parameters will be summarized by presenting descriptive statistics for the absolute values, change from baseline (and from each start of epoch) for each cohort, epoch, analysis visit and treatment group (as defined in [section 1.3](#)). Change from baseline (resp. start of epoch) will only be summarized for patients with both baseline (resp. start of epoch) and post baseline values in each epoch. There will be multiple "baseline" as one will be defined for each start of epoch. All information collected will be listed by patient and abnormal values will be flagged. In addition, shift tables based on normal ranges and incidence rates of notable abnormalities will be presented.

Creatinine clearance will be also be summarized by subgroup of Colchicine for crFMF disease cohort. Creatinine clearance will also be summarized by subgroup of CKD categories defined at baseline derived using eGFR value as below:

CKD Stage 1: ≥ 90 ml/min/1.73m²

CKD Stage 2: $60 - < 90$ ml/min/1.73m²

CKD Stage 3a-b: $30 - < 60$ ml/min/1.73m²

CKD Stage 4-5: < 30 ml/min/1.73m²

Shift in CKD stage from baseline to end of epoch 2, epoch 3 and epoch 4 will be summarized for crFMF disease cohort patients.

Notable laboratory abnormalities in adult patients (≥ 18 years of age)

Post-baseline values will be flagged as notable abnormalities as follows:

Biochemistry

1. ALT (SGPT): $> 3x, 5x, 10x$, and $20x$ Upper Limit of Normal (ULN)₁
2. AST (SGOT): $> 3x, 5x, 10x$, and $20x$ ULN₁
3. Elevation of AST and/ or ALT ($> 3x$ ULN) accompanied by elevated bilirubin ($> 1.5x$ ULN, $> 2x$ ULN)₁
4. Any elevations of bilirubin; elevated total bilirubin (TBL) to $> 2x$ ULN₁
5. Any elevations of ALP $> 1.5x$ ULN
6. Gamma-Glutamyltransferase (GGT): $> 3x$ ULN
7. Creatinine (serum): $\geq 3x$ ULN
8. Creatinine clearance (CrCl) (Cockcroft-Gault formula)₂: $\geq 25\%$ decrease from baseline
9. Triglycerides: $> 5x$ ULN

Hematology

1. Hemoglobin: ≥ 20 g/L decrease from baseline,
 < 100 g/L
2. Platelet count:
 - a. CTC Grade 1: $<$ Lower Limit of Normal (LLN) – 75×10^9 /L
 - b. CTC Grade 2: $< 75 - 50 \times 10^9$ /L
 - c. CTC Grade 3: $< 50 - 25 \times 10^9$ /L
 - d. CTC Grade 4: $< 25 \times 10^9$ /L
3. White blood cell count:
 - a. CTC Grade 1: $<$ LLN – 3×10^9 /L
 - b. CTC Grade 2: $< 3 - 2 \times 10^9$ /L
 - c. CTC Grade 3: $< 2 - 1 \times 10^9$ /L
 - d. CTC Grade 4: $< 1 \times 10^9$ /L
4. Absolute neutrophils:
 - a. CTC Grade 1: $<$ LLN – 1.5×10^9 /L

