1.13.4 Vital signs

Vital signs will be summarized by presenting descriptive statistics for the absolute values and changes from baseline (and from each start of epoch) for each cohort, epoch, analysis visit and treatment group (as defined in [section 1.3](#)). All information collected will be listed by patient and abnormal values will be flagged

Notable vital signs abnormalities in adult patients (≥ 18 years of age)

Post-baseline vital signs will be flagged as notable abnormalities as follows:

1. Systolic/Diastolic blood pressure: $\geq 25\%$ decrease or $\geq 25\%$ increase from baseline
2. Pulse: ≥ 110 bpm with $\geq 15\%$ change from baseline, or < 50 bpm with $\geq 15\%$ change from baseline

Notable vital signs abnormalities in pediatric patients (< 18 years of age)

Post-baseline vital signs in pediatric patients (at the time of the assessment) will be flagged as notable abnormalities as follows:

1. Systolic blood pressure (mmHg): >ULN and increased >20 in change from baseline or <LLN and decreased >20 in change from baseline
2. Diastolic blood pressure (mmHg): >ULN and increased >20 in change from baseline or <LLN and decreased >20 in change from baseline
3. Pulse (bpm): >ULN and increased >20 in change from baseline or <LLN and decreased >20 in change from baseline

Blood pressure normal range for patients >28 days but <18 years old are listed in below table:

Table 1-3 Blood pressure normal range in pediatric population according to current age

Age	SBP	DBP	Pulse
0 - 1 months[#]	45-80	33-52	93-182
>1 - 3 months[#]	65-85	35-55	120-178
>3 - 6 months[#]	70-90	35-65	107-197
>6 -12 months[#]	80-100	40-65	108-178
>12 months- 2 years[#]	80-100	40-70	90-152
> 2 years - 5 years	100-115	65-75	80-130
> 5 years -12 years	110-125	70-80	70-115
> 12 years -18 years	120-135	75-85	60-100

Age is age at the time of the visit.

[#]Reference values according to website: <http://www.sickkids.ca/Nursing/Education-and-learning/Nursing-Student-Orientation/module-two-clinical-care/vitals/>.

ECG

Listings and table will be provided for notable ECG abnormalities. Summary statistics will be presented for ECG variables by epoch, analysis visit and treatment group for each cohort.

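### Epoch 2 laboratory, vital-sign, ECG and by-visit CRP/SAA summaries have no specified display by randomized arm; their columns depend on flare or escape after randomization

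*SAP*

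**What the plan says.** SAP 1.3 separates two kinds of Epoch 2 output. For the first, "Treatment arms for the primary and secondary efficacy analyses will only include canakinumab 150 mg sc q4w and placebo". For the rest, "Other efficacy and safety data will be displayed in Epoch 2 in the following way", followed by three groups. The first is "Patients being randomized and not having a flare in epoch 2 (and not having received add-on dose or any up-titration". The second and third are patients with at least one flare who were up-titrated once (or had an add-on dose) or at least twice. The column labels are 150mg q4 and Placebo under no flare, then 150mg q4->300mg q4, Pla->150mg q4 and Pla->150mg q4->300mg q4 under one or more flares.

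SAP 1.13.3 applies these groups to laboratory data: "Laboratory parameters will be summarized by presenting descriptive statistics for the absolute values, change from baseline (and from each start of epoch", then "for each cohort, epoch, analysis visit and treatment group", with a pointer to section 1.3. SAP 1.13.4 does the same for vital signs: "Vital signs will be summarized by presenting descriptive statistics for the absolute values and changes from baseline (and from each start of epoch". ECG, also under 1.13.4, is by treatment group with no further definition. SAP 1.10.5 puts the by-visit CRP and SAA summaries in section 1.3 groups.

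For adverse events the wording differs: "Adverse events will be summarized by presenting, for each cohort, epoch, initial randomized treatment and treatment sequence". Table 1-2 has a column headed "Epoch 2 (restricted to initial randomized treatment arms", which is blank for CRP, PGA, adverse events, laboratory data, vital signs and ECG.

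**The concern.** Column membership is an outcome. A patient stays in the 'Placebo' column only by not flaring and not needing an add-on or up-titration through Epoch 2, and likewise for '150mg q4'. Setting those two columns side by side compares patients selected for doing well under each treatment, and the selection is probably harsher on placebo. Randomization does not protect that comparison.

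The outputs concerned are ones where this matters. Blood counts, CRP and SAA plausibly move with inflammatory activity, which is what drives the selection. A reader who wants to know what canakinumab does to neutrophils, platelets or liver tests relative to placebo over 16 weeks would find no table in the plan that answers the question as randomized.

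**Working it through.** The plan gives no figure to reproduce here, so the check is mainly a comparison of texts.

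**1. Where a randomized-arm display is specified**

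| Epoch 2 output | SAP text | By randomized arm in the text? | Randomized-arm column of Table 1-2 |
|---|---|---|---|
| Laboratory data | 1.13.3 | No | blank |
| Vital signs | 1.13.4 | No | blank |
| ECG | 1.13.4 | Not stated | blank |
| CRP and SAA by visit | 1.10.5 | No | CRP blank; no row for by-visit SAA |
| Adverse events | 1.13.1 | Yes, plus sequence | blank (conflicts with text) |
| Injection-site tolerability | 1.13.2 | Yes, plus sequence | no row |
| PGA by visit | 1.10.2.1 (also 1.10.5 by section 1.3 group) | Yes | blank (conflicts with text) |
| CRP categories before Day 15, at Day 15, at Day 29 | 1.10.5 | Yes | no separate row |
| SF-12, CHQ-PF50, SDS | 1.10.5 | Yes, plus sequence | ticked |

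Where the SAP wants both displays it says so. The laboratory and vital-sign text lacks that wording, so a second display cannot be assumed.

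**2. One patient followed through.** A placebo patient is sampled at Day 15, then receives an add-on and is up-titrated at Day 29. The Day 15 value was taken on placebo but is tabulated under Pla->150mg q4.

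**3. Size of the no-flare columns.** Input: 30 per arm per cohort (protocol section 4). The escape rates are assumed.
- Placebo, 50%, 70% or 90% flaring or escaping: 30 × 0.5 = 15, 30 × 0.3 = 9, 30 × 0.1 = 3 patients.
- Canakinumab, 15%, 40% or 60%: 30 × 0.85 = 25.5, 30 × 0.6 = 18, 30 × 0.4 = 12 patients.

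**4. Illustration of the selection.** Take a laboratory value with no drug effect and correlation ρ with a standard normal severity score, and suppose each arm's no-flare column keeps the least severe fraction q. The mean severity kept is −φ(z_q)/q, so the spurious difference (canakinumab minus placebo) is ρ × [φ(z_p)/p − φ(z_c)/c] SD, with c and p the fractions kept on canakinumab and placebo.

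| Kept, canakinumab / placebo | ρ = 0.3 | ρ = 0.5 |
|---|---|---|
| 85% / 10% | 0.44 | 0.74 |
| 60% / 10% | 0.33 | 0.56 |
| 60% / 30% | 0.15 | 0.26 |
| 40% / 10% | 0.24 | 0.39 |
| 85% / 50% | 0.16 | 0.26 |

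The range is 0.15-0.74 SD. All inputs are assumptions; the table shows only that the effect need not be small.

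**5. Share of placebo-period values under escape labels.** Assume samples at the five post-baseline visits (Days 15, 29, 57, 85, 113) and one or two pre-escape visits per escaper.
- 10% without flare or escape: 27/(27 + 3 × 5) = 27/42 = 64%, or 54/69 = 78%.
- 20%: 24/(24 + 6 × 5) = 24/54 = 44%, or 48/78 = 62%.
- 50%: 15/(15 + 15 × 5) = 15/90 = 17%, or 30/105 = 29%.

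**6. Do the groups cover everyone?** Before Day 29 an add-on is triggered by PGA or CRP alone (protocol Table 3-1), while a new flare needs PGA ≥2 and CRP ≥30 mg/L together (protocol 6.4.5). A patient with an add-on for an unresolved index flare and no new flare is barred from the first group by the add-on and, on the wording, from the others by having no flare. A patient whose first flare is seen at Day 113 has no Epoch 2 up-titration and fits no group.

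**The case against.** The strongest case for the plan is that these are descriptive tables with no test attached and that the sequence display was foreseen. Protocol section 9 names escape-sequence arms for adverse events and laboratory abnormalities, and protocol 3.2 accepts that the escape options may limit placebo-controlled safety data. The labels show the placebo origin, and all laboratory data are listed by patient. Nor is any alternative clean. Data cut at first escape leave only non-escapers at late visits, and whole-epoch data by arm mix canakinumab exposure into placebo. The add-on patients in step 6 can be placed by their column label, since an add-on leads to up-titration.

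Much of this stands. The sequence columns are no departure from the protocol and are worth keeping, and neither added display suffices alone. But scarce placebo-controlled data are a reason to show the randomized comparison, and nothing in the protocol prevents it. On coverage, the label helps with add-on patients but contradicts the group's own flare condition, and the Day 113 case remains unplaced.

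Four stronger readings are tempting, and the documents do not support them:
- A reader might infer that all Epoch 2 safety data are in outcome-selected groups. Adverse events and injection-site reactions are also shown by initial randomized treatment, and exposure-adjusted adverse event rates follow the dose actually received (SAP 1.13.1).
- A reader might extend the point to by-visit efficacy generally. PGA by visit, early CRP categories and the quality-of-life scores have randomized-arm displays. Week 16 PGA, CRP and SAA are compared by arm with escapers counted as failures (SAP 1.10.2.1).
- A reader might take Epoch 2 as the only placebo-controlled period. Epoch 3 re-randomizes canakinumab responders to q8w dosing or placebo.
- A reader might equate 80-90% of placebo patients escaping with 80-90% of placebo-period data mislabelled. Escapers contribute fewer placebo visits; step 5 gives 44-78% at those rates.

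**Conclusion.** The point holds for four outputs: Epoch 2 laboratory data, vital signs, ECG and descriptive by-visit CRP/SAA. For the first two and CRP/SAA the SAP specifies only outcome-defined groups; for ECG it names no randomized-arm display. No hypothesis test or primary or secondary result is affected.

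The size depends on an escape rate that the documents do not give. With 30 per arm and an assumed 10-50% of placebo patients free of flare and escape, the placebo no-flare column holds 3-15 patients per cohort. The 0.15-0.74 SD range is an illustration under assumed correlations and retention, not an estimate for this trial. The plan should be changed, because the remedy is cheap and the randomized comparison would otherwise be missing for these outputs.

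**What to change.** 1. In SAP 1.10.5 (CRP/SAA), 1.13.3 and 1.13.4 (including ECG), add Epoch 2 tables by initial randomized arm in two forms: over the whole epoch as randomized, and restricted to data before the first add-on or up-titration dose. Footnote the restricted form to say that late visits contain only patients who have not escaped, and the whole-epoch form to say that the placebo arm includes canakinumab exposure after escape.
2. Keep the section 1.3 sequence columns as a second, descriptive display.
3. In Table 1-2, tick the randomized-arm column for CRP (adding by-visit SAA), laboratory data, vital signs and ECG. Tick it also for adverse events and PGA, so that the table agrees with 1.13.1 and 1.10.2.1.
4. Reword the section 1.3 groups so that every patient has a column, including one with an add-on but no new flare and one with a flare first seen at Day 113 and no Epoch 2 up-titration.

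The cost is a few more descriptive tables from data already collected. No visit, assessment or test changes.
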